1.0 Research Design

1.1 Purpose/Specific Aims

The purpose of this study is to evaluate the efficacy of Nitazoxanide (NTZ), Ribavirin (RBV) and Hydroxychloroquine (HCQ) versus placebo in participants with proven SARS-CoV-2 infection who are asymptomatic or mildly symptomatic with COVID-19. Those with illness requiring hospitalization, or who present with hypoxia (PO2<92%) or shortness of breath at time of enrollment are excluded.

A. Objectives

In participants with proven SARS-CoV-2 infection who are asymptomatic or mildly symptomatic with COVID-19 randomly allocated to nitazoxanide, ribavirin plus hydroxychloroquine (NTZ, RBV + HCQ) or placebo.

Primary Objective:

To assess the rate of decline in viral load over the 10 days after randomization between participants treated with NTZ, RBV + HCQ for COVID-19 and placebo.

Secondary Objective:

- 1. To compare the proportion of participants with virus below LLOQ at day 10
- 2. To compare the proportion of participants who are asymptomatic and symptomatic at day 10
- 3. To compare the time of onset and frequency of the development of fever and other symptoms of COVID-19 in those who were asymptomatic at enrollment
- 4. To compare the progression in severity of COVID-19 symptoms (hospitalization and length of stay; admission to intensive care unit and number of days in unit; intubation, Death (any cause))
- 5. To compare the severity of disease in participants who develop symptoms of COVID-19
- 6. To compare the side effects of NTZ, RBV + HCQ compared to placebo
- 7. To determine whether baseline viral load predicts response to therapy
- 8. To assess the rate of decline in viral load over days 3 and 6 after randomization
- 9. To assess new, self-reported COVID-19 infection in household members

B. Hypotheses / Research Question(s)

We hypothesize that treatment with NTZ, RBV + HCQ decreases viral load and the progression of symptoms, or emergence of symptoms in those who are asymptomatic at baseline, in SARS-CoV-2-positive adults compared to placebo.

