Non-serious adverse events and SAEs will be determined from the time the study drug is given, throughout the treatment period and up to and including the one month follow-up period. All grade 3 or higher AEs will be recorded. Grade 1 - 2 AEs do not need to be recorded. After withdrawal from treatment, participants must be followed-up for all existing and new AEs for 60 calendar days after the last dose of trial drug and/or until event resolution. All new AEs occurring during that period must be recorded (if SAEs, they must be reported to Data Safety Monitoring Board (DSMB) and Rutgers IRB as per SOPs.).

All study-related toxicities/ SAEs must be followed until resolution, unless in the Treating Investigator's opinion, the condition is unlikely to resolve due to the patient's underlying disease.

3. Reporting of Serious Adverse Events

Investigators and other site personnel must inform the DSMB and Rutgers IRB. FDA will be informed as required accordance with the reporting obligations of 21 CFR 312.32. It is the responsibility of the principal investigator to compile all necessary information and ensure that the FDA receives a report according to the FDA reporting requirement timelines.

All SAEs meeting the criteria for expedited reporting will be reported to the Rutgers IRB within the mandated time frames. All SAEs within the safety follow-up window (e.g., within 30 days after the last dose of study medications) established in the protocol will be reported.

- 4. Clinical Safety Assessments
 - Recording of Adverse Events

Non-serious adverse events and SAEs will be determined from the time the study drug is given, throughout the treatment period and up to and including the 28-day follow-up period. All grade 3 or higher AEs will be recorded. Grade 1-2 AEs do not need to be recorded. After withdrawal from treatment, participants must be followed-up for all existing and new AEs for 28 calendar days after the last dose of trial drug and/or until event resolution. All new AEs occurring during that period must be recorded (if SAEs, they must be reported to the Data Safety Monitoring Committee and Rutgers IRB).

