- 4. Proportion of participants with progression of severity of COVID-19 symptoms (hospitalization and length of stay; admission to intensive care unit and number of days in unit; Intubation; Death (any cause))
- 5. Comparison of severity of disease in participants who develop symptoms of COVID-19 at all timepoints
- 6. Assessment of medication toxicity as measured by standard metrics
- 7. Q-T interval from baseline of > 60msec or QT > 500 msec)
- 8. Number of participants with undetectable viral load and absence of symptoms
- 9. Rate of decline in viral load at study days 3 and 6
- 10. New, self-reported COVID infection in household members

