1.4 Preliminary Data

There are data supporting the antiviral activity of NTZ, RBV and HCQ as single agents as summarized in Section 1.2. There is no previous human experience with this triple combination.

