1.6 Study Variables

A. Primary Outcome:

Viral load at 10 days post randomization

B. Other measures

Age, Gender Race/ethnicity BMI Co-morbidity:

- Diabetes mellitus
- Hypertension
- Chronic bronchitis, emphysema, or chronic obstructive pulmonary disease (COPD)
- Other lung disease
- Coronary artery disease, peripheral artery disease, angina, or heart attack (myocardial infarction)
- Congestive heart failure
- Stroke or transient ischemic attack (TIA)
- Atrial fibrillation
- Cancer other than non-melanoma skin cancer
- Chronic kidney disease (CKD)
- Crohn's disease, ulcerative colitis, or inflammatory bowel disease (IBD)
- Rheumatoid arthritis (RA), psoriasis, systemic lupus, multiple sclerosis, or another autoimmune disorder
- Allergic rhinitis

Medications Symptoms Household infection (confirmed or suspected)

List variables of interest

Treatment Variables:

- Treatment Compliance
- Adverse Events (number/percentage/grade)

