1.9 Data Collection

A. Primary Data Collection

Data collection will occur at a baseline visit with follow-up data collected over the subsequent month as described below.

Location: Study site visits (baseline, day 14 & day 28) will take place at the designated RWJMS study location at [name] which is an Institutional Biosafety Committee (IBC) approved location to meet with SARS-Cov-2 positive individuals. Consent and all questionnaires will be completed electronically online. This questionnaire will include items on health and medical history, lifestyle, employment and patient contact, and demographics. At baseline, contact information (e-mail/phone) for the participant will be collected as well as contact information of 2 individuals who know the participant well who we can reach out to in case the participant falls ill.

Follow-up questionnaires will be administered daily for 10 days and on day 28 after entering the study. Follow-up questionnaires will include items on symptoms of COVID-19, reactions to the study medications and health status of household members since the last questionnaire Up to 3 daily automated reminders will be sent to remind participants to complete the surveys. In addition, participants will self-report their body temperature, PO2, and pulse daily through REDcap, daily for the first 10 days of the study period. Participants will receive automated email/text reminders to record this information daily. We will also call on days 3, 6 and 10 to confirm self specimen collection, check medical status and study drug dosing (on days 3 & 6) and questionnaire completion compliance. On day 14 participants will return for a blood draw and to return the ZIO AT monitoring device. On day 28, participants will return to the clinic for a final symptom assessment, a blood draw for immune function and CBC, pregnancy test, if applicable and final study drug accountability.

- Process of Data Collection: All in-person data collection will be overseen by the clinical study coordinator team conducting study visits, with questionnaires self-administered by participants. The blood specimens will be collected at the in-person visits (baseline, day 14 & 28). Participants will be responsible for reporting their own daily temperatures, PO2 and pulse.

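### The adverse event record supports only a grade 3+ comparison, although objective 6 compares side effects without a grade limit and mostly mild reactions are expected

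*Combined protocol and SAP*

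**What the plan says.** Section 1.3 C.2 sets the threshold: "All grade 3 or higher AEs will be recorded". The next sentence is "Grade 1 - 2 AEs do not need to be recorded". Section 1.3 C.4 repeats both rules almost word for word.

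Both paragraphs then turn to follow-up after withdrawal from treatment, where they say "All new AEs occurring during that period must be recorded" and give no grade limit.

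Other parts of the protocol ask for more than a grade 3+ record:

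- Secondary objective 6 (section 1.1) is "To compare the side effects of NTZ, RBV + HCQ compared to placebo".
- Secondary endpoint 6 (section 1.3 F) is "Assessment of medication toxicity as measured by standard metrics"; the metrics are not named.
- Section 1.6 lists "Adverse Events (number/percentage/grade" among the treatment variables.
- The AE definition in section 1.3 C.1 gives nausea as an example of a symptom that counts as an AE.

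On prior knowledge, section 1.4 says "There is no previous human experience with this triple combination". Section 1.9 describes follow-up questionnaires on days 1 to 10 and day 28 that include items on "reactions to the study medications and health status of household members since the last questionnaire".

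**The concern.** Tolerability is one of the main things a first study of a new combination can report. Most reactions that the protocol leads one to expect from a five-day oral course are gastrointestinal or neurological and mild. If staff follow the recording rule as written, these reactions need never appear as AEs, and objective 6 becomes a grade 3+ comparison without the protocol saying so.

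Optional recording is also awkward in its own right. The counts of grade 1-2 events would depend on how individual staff use their discretion. Masking should keep that from favoring one arm, but it does not make the counts complete or the percentages interpretable. A near-empty AE table could then be read as good tolerability when the threshold was part of the reason.

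**Working it through.** The plan states no sample size, power or alpha for safety, so there is no figure of its own to reproduce. The check has two parts.

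**1. What each source delivers for objective 6**

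| Source | Section | Covers grade 1-2 reactions? |
|---|---|---|
| AE record | 1.3 C.2, C.4 | Grade 3+ required; grade 1-2 optional |
| New AEs after withdrawal from treatment | 1.3 C.2, C.4 | Required, no grade limit; conflicts with the row above |
| Questionnaires, days 1-10 and 28 | 1.9 | Ask about drug reactions; grading, entry as AEs and use in analysis not stated |
| Blood count and metabolic panel at baseline, day 14, day 28 | 1.3 A, 4.7 E | Yes, for laboratory effects |
| QT through day 10 | 1.3 B, 4.7 E | Yes, for QT |

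The sentence on new AEs can be read in two ways: it covers only participants who stop early, or everyone after the last dose. On either reading, grade 1-2 events during treatment remain optional. No grading scale is named anywhere, and the analysis section (6.1) does not list AEs among its example outcomes. Gastrointestinal and nervous-system reactions therefore have only the questionnaire as a sure source, and its role is undefined.

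**2. Scale**

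Inputs from the documents:

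- 35 participants per arm (section 1.5).
- Hydroxychloroquine abdominal pain and nausea at 10% or more; nitazoxanide side effects described as generally mild and transient (section 4.7 A).
- Diarrhea in 17 of 211 (8%) on high-dose nitazoxanide and 7 of 212 (3%) on placebo in the cited influenza trial (section 1.2). The protocol does not say which grades were counted.

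Assumed, because no document gives grade 3+ rates: a risk p from 1% to 5% in the active arm. For the tests, a two-sided 0.05 level is also assumed.

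*Mild reactions at stake:* 35 × 0.10 = 3.5 and 35 × 0.08 = 2.8 affected active participants per reaction. If these are grade 1-2, the AE record need hold none of them.

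*Grade 3+ record:* expected participants = 35p; chance of none = (1 − p)^35.

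| Assumed p | Expected in 35 | Chance of none |
|---|---|---|
| 1% | 0.35 | 70% |
| 2% | 0.70 | 49% |
| 3% | 1.05 | 34% |
| 5% | 1.75 | 17% |

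*Half-enrollment safety review (section 6.3 B):* with about 18 per arm, the chance of none is 0.99^18 = 83% at 1% and 0.95^18 = 40% at 5%.

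*Evidence needed for a difference:* with no events on placebo and a on active, the two-sided Fisher p is 2 × C(35,a)/C(70,a). For a = 5 this is 0.054; for a = 6 it is 0.025. Six active participants would be needed. Power for 5% v 1% is about 0.5%.

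*What full recording would add:* for diarrhea at 8% v 3%, the expected counts are 2.8 and 35 × 0.03 = 1.05, and Fisher power is about 2%. Even an assumed 30% v 10% gives about 46%. The gain is in description, with only a limited gain in testing.

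**The case against.** The best case for the plan is that mild toxicity is not lost. The wording permits grade 1-2 recording. Questionnaires on days 1 to 10 and day 28 ask about drug reactions. Hemoglobin, chemistry and QT are measured whatever the AE grade, and QT has its own endpoint. Vomiting and diarrhea are also captured as COVID-19 symptoms. Endpoint 6 is not tied to the AE form. With 35 per arm, full recording would still leave most single reactions untestable, and the one comparison quoted above is selective: in the same influenza trial, headache ran the other way (8% on high dose, 11% on placebo).

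Most of this stands, and it rules out several stronger readings that a reader might infer:

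- That grade 1-2 events will not be recorded, or that staff are told to leave them out. The text makes recording optional.
- That objective 6 cannot be delivered. Grade 3+ events, questionnaire reactions, laboratory values and QT can all be compared by arm.
- That a fall in hemoglobin would be missed. It is measured at three time points.
- That the data safety monitoring board (DSMB) will not see questionnaire reactions. Section 6.3 does not say so; it leaves the matter open.
- That a finding of no difference would be produced by the recording rule alone. Sample size is a main cause too.

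What the objection does not answer is the missing link: no section turns questionnaire reactions into graded AEs or names them as the data for objective 6.

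**Conclusion.** The point holds in a limited form. The required AE record is cut off at grade 3, so it supports only a grade 3+ comparison and a truncated grade variable, while objective 6 and section 1.6 carry no such limit. Under the assumed 1% to 5% risks, that record would probably hold zero to two affected participants in the active arm. The range rests on assumed rates, because the protocol gives none. The expectation that most reactions fall below grade 3 is an inference from the protocol's descriptions, which do not grade them. Two related defects are textual and need no assumption: the grade rule conflicts with the sentence requiring all new AEs, and the role of questionnaire reactions is undefined. This should be corrected, but it does not threaten the primary analysis.

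**What to change.** - In both section 1.3 C.2 and C.4, replace the grade rule with a requirement that AEs of any grade be recorded and graded on a named scale. Keep grade 3+ as a reporting subset.
- State that the sources are the existing daily questionnaires and the AE reviews on days 3, 6, 10 and 28. Say how reactions that overlap with COVID-19 symptoms, such as diarrhea, are counted.
- In section 6.1, name the AE summary for objective 6: participants with at least one event, by arm and grade, presented mainly as description given the low power.
- Reconcile the new rule with the sentence on all new AEs, and reconcile the safety windows in section 1.3 C: 60 days in C.2, 30 days in C.3 and 28 days in C.4.

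If the sponsor prefers to keep the threshold, objective 6 and section 1.6 should be limited to grade 3+, with a statement of how questionnaire reactions are graded and analyzed.

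The cost is protocol wording and modest extra data entry for 70 participants. No visit or test is added.

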 Adverse Events Based on Signs and Symptoms When collecting AEs, the recording of diagnoses is preferred (when possible) to recording a list of signs and symptoms. However, if a diagnosis is known and there are other signs or symptoms that are not generally part of the diagnosis, the diagnosis and each sign or symptom will be recorded separately.

D. Data Points

Case Report Forms

Completion of the electronic case report forms (eCRFs) will be done in accordance with the instructions outlined in the study specific data capture plan. All eCRFs are considered the primary

data collection document for the study and are stored in REDCap in a confidential format. Only key personnel who are delegated in the delegation of authority log are permitted to make entries, changes, or corrections in the eCRF. All users will complete user training, as required or appropriate per regulations. An audit trail will be maintained automatically by the electronic CRF management system.

Data Points to be collected:

- Baseline medical history
- Treatment compliance
- Daily temperatures
- Symptoms of disease
- Adverse events
- Concomitant medications
- Any standard of care treatments or procedures to manage COVID-19
- Viral load from saliva specimen
- Viral load from mid-turbinate self-nasal swab
- SARS-CoV-2 infections confirmed or suspected in household members

Data Submission Timeline and Forms

Completion of eCRFs will occur within 72 hours of study time point unless otherwise indicated. Baseline (pre-study) eCRFs (e.g., enrollment, medical history, concomitant medications, etc.) will be completed no later than 24 hours after the start of treatment.

E. Study Duration

Study participants will be treated for five (5) days and will then remain on follow-up for up to 28 days after entry into the study. The estimated time to complete the entire study including data analysis is 3-6 months

F. Endpoints

Primary endpoint:

1. Rate of decline in viral load over the 10 days after randomization

Secondary:

- 1. Proportion of participants with virus below LLOQ at day 10
- 2. Proportion of participants asymptomatic at day 10.
- For those who were asymptomatic at baseline: Progression to symptoms--presence or absence of key symptoms: fever ≥ 100.4^o F (38 ^o C); sore throat, cough, shortness of breath, myalgias, vomiting or diarrhea, or change in smell or taste

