1.5 Sample Size Justification

Primary outcome:

Rate of decline in viral load. We expect a gradual decay in viral loads (depending on when in the infection's natural history participants are enrolled. Participants will be detected as being SARS-CoV-2-positive by our screen at varying points in the infection (some early, some late). Based on the 4 manuscripts with measurements, including Hung et al ³¹ and Gautret et al ¹⁹, we can calculate an expected decline rate. One outcome would be a greater than expected fall in viral load in the active arms vs the SoC arm (e.g., 0.3 log₁₀ /day greater decline =0.9 log₁₀ in 3 days).

We will compare rate of decline in viral load Arm 1 (NTZ, RBV + HCQ) to Arm 2 (placebo) with the aim of determining if the combination of NTZ, RBV + HCQ is superior to placebo. We plan to enroll 35 participants in each arm of the trial for a total of 70. We assume data are collected at baseline and 3, 6 and 10 days after enrollment.

Power calculations were obtained from simulated data, where:

- Baseline log10 VL was generated from uniform (3,9) distribution (i.e., at baseline, people were equally likely to have log10 VL anywhere from 3 to 9. This is consistent with Hung et al ³¹
- For the control group, average change per day was set to either -0.3 or -0.4. In Hung et al ³¹ it appears to be about -0.37.
- For the treatment group, the average decline per day was greater (steeper) than the control group by either 0.2 or 0.3. In Hung et al ³¹the difference in slopes appears to be about 0.2
- Within person SD was set to either 0.5 or 1.
- SD of the slope between individuals was set to 0.2. In Hung et al ³¹ the within-group IQR of log10 VL was relatively small, so we do not expect a large amount of variation in slopes between participants.

Power was calculated using the following steps: (1) generate 1000 data sets in each scenario; (2) fit random slope and intercept models to the simulated data; (3) record the proportion of times that the test of the interaction between treatment and slope was rejected.

		treatment effect		
Slope SoC group	SD	-0.2	-0.3	
-0.3	0.5	94	99	
-0.4	0.5	94	99	
-0.3	1	87	99	
-0.4	1	84	99	

Results: Power (%) based on a sample size of 30 per group

In all of these scenarios we would have >80% power to detect a difference in the slope between groups.

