1.8 Specimen Collection

A. Primary Specimen Collection

The research specimens collected will be for:

- 1. Viral load
- 2. Antibody testing
- 3. Safety (CBC and chemistry)

Types of Specimens:

- Mid-turbinate self nasal swab will be collected at baseline and days 3, 6 and 10
- Blood specimen will be collected at baseline, day 14 and day 28
- Annotation: Specimens will be uniquely identified and marked with the participant's study ID and study time point. All primary collection devices (blood and nasal swab kits) will have a unique barcode that is linked to the participant study ID at the time of collection and sample registration.
- Transport: Nasal-swabs specimens (live virus is fully deactivated by the transport media) will placed in the packing materials supplied by the research laboratory (TGen) or designee shipped to Altasciences via Fed Ex promptly following specimen collection at the clinic and at home. The nasal swab specimens will be batched at Altasciences and shipped to TGen on a frequency to be determined by study enrollment. All shipping material, instructions and transport supplies will be provided to the participant within the collection kit. All blood specimens will be collected during clinic visits and transported for testing in accordance with institutional policy. Blood for clinical analyses (cbc, chem panel, magnesium will be directly transported to the RWJUH laboratory by the study staff. Blood drawn for antibody testing will be packaged and sent to RUCDR via UPS, using the materials and instructions provided by RUCDR. These samples will be processed, frozen, and stored at RUCDR until transport to the [name] Lab for analysis.
- **Processing**: All specimen processing will be in accordance with institutional policy.

- Storage: The blood specimens and the nasal swab specimens will be stored at their respective laboratories until the time of testing.
- Disposition: The antibody blood specimens and nasal swab specimens will be maintained until the end of study. Leftover specimens may be de-identified and may be used for other future research, e.g., validating viral load measurements with improved technologies or viral sequencing analysis.
- B. Secondary Specimen Collection N/A

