The participant will then come to the study location at [name] to complete final screening for the trial eligibility. P02 will be measured and 6 lead portable electrocardiogram will be performed; if PO2<92% or QT interval is QTc interval > 450 mSEC the participant will be excluded. Females of childbearing potential will have a urine test to confirm that they are not pregnant.

Inclusion Criteria

- 1. Documented SARS-CoV-2 infection by qPCR assay without symptoms or with mild symptoms consistent with COVID-19 performed within the past 7 days
- 2. Age ≥21

Exclusion Criteria

- 1. COVID-19 symptoms requiring hospitalization
- 2. PO2 < 92%
- 3. Short of breath at time of enrollment
- 4. Retinal eye disease
- 5. Known glucose-6 phosphate dehydrogenase (G-6-PD) deficiency
- 6. Known chronic kidney disease, stage 5 or receiving dialysis
- 7. Current use of:
 - Class 3 AAD (amiodarone, dronaderone, dofetilide, sotalol)
 - Class 1A AAD (procainamide, quinidine, disopyramide)
 - Flecainide
 - SSRI: citalopram (Celexa), Escitalopram (Lexapro)
 - chlorpromazine
 - Cilostazol (Pletal)
 - Donepezil (Aricept)
 - Droperidol
 - Fluoconazole
 - Methadone
 - Ondansetron (Zofran)
 - Thioridazine
 - Macrolides (clarithromycin, erythromycin)
 - Fluroquinolones (ciprofloxacin, levofloxacin, moxifloxacin)
 - Tamoxifen citrate
- 8. Pregnancy or women who are breast feeding
- 9. Inability to tolerate oral medications
- 10. Allergy or prior adverse reaction to either hydroxychloroquine sulfate, ribavirin, or nitazoxanide
- 11. Allergy to adhesives
- 12. QTc interval > 450 mSEC for men and women
- 13. History of Torsade de Pointes VT or prior cardiac arrest or congenital long QT interval
- 14. Non-English-speaking

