6.0 Data Management Plan

6.1 Data Analysis

We will follow intention-to-treat principles and analyze the groups as randomized. A summary table of baseline variables will be created with means and standard deviations for continuous variables or percentages for categorical variables, all stratified by treatment group.

Primary outcome. We will have repeated measures of log10 VL for each participant. These measurements will occur on day 0 (baseline) and at about days 3, 6 and 10. We will fit a linear mixed effects model, where log10 VL is the outcome, indicators for treatment group (SoC reference), time, and treatment by time interactions are the predictors. The model will include a random slope and intercept, to account for within participant correlation. The robust sandwich variance will be used to estimate standard errors. Because we are estimating within participant changes over time from randomization, we can estimate a treatment effect at any particular day. Our primary hypotheses involve the change over time, which we will assess with the treatment by time interaction terms. If participants drop out from the study

before the day 10 visit, we will use all of their preceding data. Linear mixed effects models rely on the assumption that missing data are missing at random.

Secondary outcomes. For binary outcomes, such as progression to having symptoms, intubation, death, hospitalization, and admission to intensive care unit, we will fit logistic regression models. The covariates will include the treatment group indicators. We will report odds ratios and 95% confidence intervals. For change variables, such as change in viral shedding or change in Q-T interval, we will fit linear mixed effects models (similar to primary outcome).

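### Secondary 1 (below LLOQ at day 10) is analysed without baseline viral load as a covariate, which costs precision that the day-0 swab could recover

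*Combined protocol and SAP*

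**What the plan says.** All references are to the combined protocol and SAP.

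- **Endpoints (1.3 F).** Secondary 1 is "Proportion of participants with virus below LLOQ at day 10". Secondary 8 is "Number of participants with undetectable viral load and absence of symptoms". Neither refers to the starting load, and no value is given for the LLOQ.
- **Entry (4.1).** The virological criterion is "Documented SARS-CoV-2 infection by qPCR assay without symptoms or with mild symptoms consistent with COVID-19 performed within the past 7 days". Quantifiable virus on the day-0 swab is not required.
- **Expected spread (1.5).** "Baseline log10 VL was generated from uniform (3,9) distribution", a range of 6 log10. The same section says "Participants will be detected as being SARS-CoV-2-positive by our screen at varying points in the infection (some early, some late".
- **Assay timing (1.8).** "The nasal swab specimens will be batched at Altasciences and shipped to TGen on a frequency to be determined by study enrollment". The day-0 load is therefore not known at randomization and cannot screen anyone out.
- **Allocation (1.3).** Randomization is stratified by presence of mild symptoms, not by viral load.
- **Analysis (6.1).** For binary secondary outcomes: "The covariates will include the treatment group indicators". No other covariate is named.
- **Objective 7 (1.1).** It asks whether starting load predicts response to treatment. Section 6.1 gives no analysis for it.

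**The concern.** Secondary 1 scores everyone against one fixed level at day 10, wherever they started. With a 6-log10 spread at entry, a participant starting at 4 log10 has a much shorter way to go than one starting at 8. The treatment-only logistic model leaves that known variation unexplained. Nothing in the design balances load between two arms of 35, so a chance imbalance passes directly into the odds ratio. The primary mixed model is better protected because its random intercept takes up the starting level; the logistic model has no counterpart. In addition, anyone already below LLOQ at day 0 who stays there counts as cleared in either arm, which dilutes the contrast and makes the clearance proportion harder to read.

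**Working it through.** **Inputs from 1.5.** Baseline Uniform(3,9) log10. Control slope -0.3 or -0.4 per day, with about -0.37 read from the cited trial. Slope difference 0.2 or 0.3. Between-person slope SD 0.2. Within-person SD 0.5 or 1. Swabs on days 0, 3, 6 and 10. The power table uses 30 per group; the planned size is 35 per arm. *Assumed because not stated:* two-sided alpha 0.05, and LLOQ of 2 or 3 log10.

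**Step 1: reproduce the plan's own power.** The plan states power only for the primary slope comparison.
- Days 0, 3, 6, 10 have mean 4.75, so Sxx = 22.5625 + 3.0625 + 1.5625 + 27.5625 = 54.75.
- With SD 0.5, per-person slope SD = sqrt(0.2² + 0.5²/54.75) = 0.211.
- SE of the difference = 0.211 × sqrt(2/30) = 0.0545.
- Power = Φ(0.2/0.0545 - 1.96) = Φ(1.71) = 95.6%. A noncentral t version gives 95.0% and simulation 95.1%. The plan states 94%.
- Using the t or simulation version, seven of the eight cells agree within 2 points. The exception (control -0.4, SD 1, effect 0.2) is stated as 84% and computes to about 88-89%. It does not bear on this point.

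**Step 2: how much day-10 variation is due to baseline.** Within an arm, day-10 variance has three parts:
- baseline: (9 - 3)²/12 = 3.0
- slope: 10² × 0.2² = 4.0
- within-person: 0.25 or 1

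The total is 7.25 or 8.0. Baseline accounts for 3.0/8.0 = 38% to 3.0/7.25 = 41%. Slope variation accounts for 4.0/8.0 = 50% to 4.0/7.25 = 55%.

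**Step 3: success by starting level.** For starting load b and daily slope m, P(success) = Φ((LLOQ - b - 10m)/S), with S = sqrt(4.0 + within-person variance). Control arm, slopes -0.3 and -0.4, LLOQ 2-3:

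| Baseline log10 VL | Success at day 10 |
|---|---|
| 3-5 | 67-92% |
| 5-7 | 31-68% |
| 7-9 | 8-33% |

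Within a scenario the gap between the lowest and highest band is about 60 points. The overall treatment difference at effect 0.2 is 22-28 points.

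**Step 4: power for Secondary 1 at 35 per arm.** Day-10 values were simulated from the same inputs with control slope -0.37, and the treatment term tested in logistic regression:

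| Slope difference | Treatment only | Plus day-0 log10 VL |
|---|---|---|
| 0.2 | 57-63% | 65-77% |
| 0.3 | 85-92% | 89-97% |
| 0 (null) | 3-5% | 3-5% |

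Ranges run over LLOQ 2-3 and within-person SD 0.5-1. A separate run with control slopes -0.3 and -0.4 and a likelihood-ratio test gave 60-68% rising to 66-81% at 0.2 (gain 6-17 points). At 0.3 it gave 86-94% rising to 90-98% (gain 4-6 points). Its type I error was 5-6% for both models.

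**Step 5: share already below LLOQ at day 0.**
- If Uniform(3,9) holds at baseline, as 1.5 states, no true load is below 3. About 0-7% would still measure below LLOQ through within-person variation alone.
- If that distribution is instead assumed to hold at a qualifying test 0-7 days earlier, up to 0.37 × 7 = 2.6 log10 could be lost before entry. The share is then 9-23%, and power at effect 0.2 is 35-55% without the covariate and 44-67% with it.

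**The case against.** The strongest defence is that nothing here is invalid. Allocation is randomized, type I error is held without adjustment, and an already-clear participant counts the same way in both arms. The plan claims no power for any secondary endpoint. The sentence in 6.1 does not forbid further covariates, and objective 7 shows that baseline load was in view. All of this stands, and it limits the point to precision and interpretation. It does not remove it: no adjustment is pre-specified, and choosing a covariate after unblinding is what pre-specification is meant to prevent.

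Four stronger readings are tempting, and the documents do not support them.

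- *The odds ratio is biased.* Randomization balances load in expectation. Chance imbalance in 70 participants is a matter of variance.
- *Starting level dominates the outcome.* Baseline explains about 40% of day-10 variance, less than between-person slope variation (50-55%).
- *A participant starting at 9 log10 fails whatever the treatment does.* At effect 0.2 the treated mean at day 10 is 9 - 5.7 = 3.3, with S about 2.1-2.2. Success is 26-45% on treatment against 5-15% on control.
- *A sizeable share is already clear at entry.* The entry rule makes this possible, but 9-23% requires moving the distribution in 1.5 to the qualifying test and assuming steady decline from then on. No section describes load between that test and day 0.

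It is also fair to say that the gain is modest, about 4-6 points, at the larger of the plan's two effects.

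**Conclusion.** The point holds as a loss of precision in the first-listed secondary endpoint. Baseline load is a strong predictor that is measured on everyone and left out of the model. At the plan's smaller effect, adjustment moves power from about 57-63% to 65-77%; at the larger effect, from about 85-92% to 89-97%. The validity of the test is not in question.

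These figures rest on the simulation inputs in 1.5, an assumed LLOQ of 2-3 log10 and an assumed two-sided alpha of 0.05. The share below LLOQ at day 0 cannot be settled from the documents. Secondary 8 was not computed because the plan gives neither symptom rates nor a time point for it; the same reasoning applies, but the gain is unknown. The change is worth making, though the trial's primary conclusion does not depend on it.

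**What to change.** In 6.1, state that the logistic model for Secondary 1 will include day-0 log10 viral load as a covariate, with values below LLOQ set to one fixed, pre-specified value, and that all randomized participants are kept. Apply the same rule to Secondary 8. Note that the adjusted odds ratio is conditional on baseline load, so it is a different quantity from the unadjusted one and the two should not be compared as if they were the same.

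Report, by arm, the number below LLOQ at day 0. This lets readers see how much day-10 clearance preceded treatment. It does not change how those participants are scored.

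The cost is about two sentences in 6.1 and one row in the baseline table. The day-0 swab is already collected, so no visits, specimens or participants are added and no clinical procedure changes. The text should be fixed before unblinding.
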